5. PHARMACEUTICAL INFORMATION

5.1. Agent Accountability

The study drug will be provided by the sponsor.

The study site will acknowledge receipt of study drug supplied by the sponsor by returning the appropriate documentation form to confirm the shipment condition and content. Any damaged shipments will be replaced.

An accurate drug disposition record will be kept, specifying all study drug received, dispensed, returned to the sponsor, and disposed of by the study site. This drug accountability record will be available for inspection at any time, and at the completion of the study, the original drug accountability record will be available for review by the sponsor upon request.

5.2. Mode of Action

The mechanism of antiviral activity of EIDD-2801 is 'lethal mutagenesis', a concept that is predicated on increasing the viral mutation rate beyond a biologically tolerable threshold, resulting in impairment of viral fitness and leading to viral extinction.

The specifics of the mechanism are as follows: EIDD-2801 is rapidly taken up by cells and the 5'isopropylester cleaved to liberate EIDD-1931, which is in turn phosphorylated to EIDD-2061 by host kinases. The 5'triphosphate, EIDD-2061, acts as a competitive, alternative substrate for virally-encoded RNA-dependent RNA polymerases, and EIDD-2061 is incorporated into nascent viral RNA. Owing to the ability of the N4hydroxycytosine base of EIDD-1931 to tautomerize, EIDD-2061 can pair with either guanosine or adenosine, and consequently can substitute for either cytidine triphosphate (CTP) or uridine triphosphate (UTP), respectively. This results in an accumulation of mutations, which increase with each cycle of viral replication. The process whereby the mutation rate is increased by exposure to a drug is referred to as viral decay acceleration and results in viral ablation.

Significant work has gone into validating this mechanism of action for EIDD-2801/1931, and it has been shown for MERS-CoV, VEEV, and influenza A virus (IAV) that viruses grown in the presence of EIDD-1931 have significantly increased levels of transition mutations. Multi-log decreases in virus yields were observed after treatment with EIDD-1931. Additionally, it was demonstrated for VEEV that the infectivity of virions formed in the presence of EIDD-1931 decreases from approximately 20% to <0.2%, and that the infectious virions are significantly impaired in their replication ability. As a consequence of this mechanism of action, the generation of drug-resistant escape mutants is practically impossible. This same effect was demonstrated for CoV and influenza virus. Furthermore, given the unique mechanism of action, EIDD-2801 is expected to be active against viruses resistant to other antiviral agents which have a different mechanism of action. The only data generated to date regarding the activity of EIDD-1931 against viruses resistant to other nucleoside analogs found that EIDD-1931 was active against CoV resistant to remdesivir in cell culture assays.

As an alternative or additional mechanism of action, it has been theorized that incorporation of EIDD-2061 into viral genomic RNA can change the thermodynamics of RNA secondary structure and

Version: 7.0

thus decrease the efficiency of the promoter regions involved in RNA genome replication. Further details regarding the mechanism of action of EIDD-2801 are provided in the IB.

5.3. Description

EIDD-2801 is a white to off white solid.

EIDD 2801 (100- and 200-mg capsules) and matching placebo will be supplied as dry filled capsules for oral administration, along with the batch/lot numbers and Certificates of Analysis. Doses of EIDD-2801 or matching placebo will be administered as combinations of 100- and 200-mg capsules in such a way as to preserve the study blind and as appropriate for the dose level.

5.4. Packaging

The study drug will be labeled in accordance with regulatory requirements and will be stored according to the instructions on the label, in a location that is locked with restricted access.

5.5. Storage

Study drug should be stored in a secure, locked, restricted access facility at controlled room temperature defined as 15°C to 25°C (59°F to 77°F). Excursions are permitted up to 30°C (86°F) for up to 24 hours. If excursions occur which are outside of this range, the pharmacy staff should contact the sponsor to determine the course of action. Additional stability data may be available which would allow continued use of the study drug, or study drug may need to be replaced.

5.6. Route of Administration

EIDD-2801 is administered orally.

5.7. Participant Care Implications

Participants who receive EIDD-2801 during this study will be monitored for AEs and other safety findings. Virology samples will be collected and SOC for COVID-19 will be administered. Participation in this study will not alter clinical decisions with regards to hospital treatment, discharge, or outpatient management.

Participants who are admitted and enrolled at one participating site who are then transferred to another participating site, will continue to remain on study and will continue to receive study drug or placebo as initially assigned.

5.8. Returns and Reconciliations

At completion of the study, study drug will either be disposed of at the study site according to the study site's standard operating procedure or will be returned to the sponsor with the appropriate documentation. The site's method of destroying sponsor-supplied study drug must be agreed to by the sponsor. The site must obtain written authorization from the sponsor before any sponsor-supplied study drug is destroyed, and study drug destruction must be documented on the appropriate form.

5.9. Pharmacokinetics

Pharmacokinetic analysis will be performed in a subset of study participants and will be conducted based on local laboratory capacity. The PK secondary (plasma) and exploratory (PBMC) objectives will be limited to clinical sites that are able to participate, including but not limited to

Blood samples will be collected for plasma isolation and PBMC preparation to characterize EIDD-2801/EIDD-1931 and EIDD-2061 PK parameters. Previous studies demonstrated an EIDD-1931 PK t_{1/2} of 0.969 hours in healthy human subjects (EIDD-2801 Investigator's Brochure, V3.0, 2020). The calculated t_{1/2} of the EIDD-2061 metabolite is 4 hours, based on *ex vivo* incubation studies. Based on currently available PK data, additional pharmacologic analyses will be conducted in a subset of SARS-CoV-2-infected individuals.

Post-enrollment and initiation of therapy, and after an overnight fast (i.e., no food or liquid except for water after midnight), PK assessment will initiate on Day 3 for participants who are still inpatients. For EIDD-2801/EIDD-1931 analysis, blood will be collected on Day 3 at pre-dose, as well as 0.5 hours, 1.5 hours, 3 hours, 6 hours, 8 hours, on Day 3 and 24 hours post-Day 3 dose on Day 4 where possible. If a participant is scheduled to be discharged, then PK samples should be collected at all scheduled time points up to the time of discharge. In addition, if a participant is discharged prior to the 24-hour PK sample, a 12-hour PK sample on Day 3 should be collected, when possible.

Blood sampling for PBMC isolation and EIDD-2061 measurements will occur at pre-dose, as well as 0.5 hours, 1.5 hours, 3 hours, 6 hours, 8 hours, and 24 hours post-dose on Day 3 where possible, as described in the previous paragraph. Time of dose will be recorded on eCRFs.

Sparse PBMC sampling will be conducted to estimate EIDD-2061 t_{1/2} and AUC_{tau}. C_{max} and t_{max} will be estimated. PK analyses in PBMC will be conducted as an exploratory objective to understand and characterize parent: metabolite (EIDD-1931:EIDD-2061) ratios at each time point, as well as persistence of EIDD-2061 after EIDD-1931 clearance from plasma.

Samples may be collected within a \pm 15 minute window (for timepoints up to 3 hours post dose), \pm 30 minutes (for timepoints 6-8 hours post dose); and \pm 1 hour (for timepoints 12-24 hours post dose).

Full processing details for plasma and PBMC PK will be provided within the study specific manual.

Sample Analysis

Plasma PK analysis will be performed at

. PBMC analysis will be performed under the control of the

The details of sample collection and analysis will be included in the Laboratory Manual and standard operating procedures (SOPs). Raw data will be archived at the bioanalytical site.

Version: 7.0

6. STATISTICAL CONSIDERATIONS

6.1. Sample Size and Power Considerations

We will test the hypothesis that EIDD-2801 will result in a larger proportion of NP swabs from recipients becoming undetectable (below the LOD of the assay) for SARS-CoV-2 RNA at Day 5 of EIDD-2801 administration compared to placebo. Participants receiving the same dose across the study parts will be pooled together in the final analysis. It is expected that 14 or more participants will receive EIDD-2801 in the higher dose groups, and at least 14 participants will receive placebo across the study parts. The power calculations were based on an individual dose arm versus placebo comparison, using a Fisher's exact test. Based on previous data (Wolfel, *Nature*, 2020), if we assume that 80% of the placebo arm and 20% of an EIDD-2801 arm are detectable at Day 5, we will have 83% power to detect a difference with α =0.05.

6.2. Statistical Analysis

6.2.1. Analysis Populations

Screened

All patients who consent to participate and who undergo screening will be included in the Screened population.

Safety

All patients treated with at least one dose of study drug will be included in the Safety population. Safety patients are analyzed according to their actual treatment received.

Intent-to-treat Set

The Intent-to-treat set (ITT) will consist of all randomized patients. ITT patients are analyzed according to their randomized treatment.

Efficacy Analysis Set

The Efficacy Analysis Set (EAS) will consist of all participants treated with at least one dose of study drug and with at least 1 post baseline assessment of SARS-CoV-2 RNA in NP swabs by qPCR. Efficacy analysis set participants are analyzed according to their actual treatment received.

Per Protocol Set

The Per-Protocol Set (PPS) will consist of all participants in the ITT population who do not have any important protocol deviations leading to exclusion from the PPS.

Protocol deviations are defined as any change, divergence, or departure from the study design or procedures defined in the study protocol. Important protocol deviations are a subset of protocol deviations and may significantly impact the correctness, accuracy, and/or reliability of the study data or that may significantly affect a subject's rights, safety, or well-being.

Version: 7.0

Version: 7.0 18 May 2021

Only those important protocol deviations considered to have a major effect on efficacy will lead to complete exclusion of the participants from the PPS. Details will be provided in a Statistical Analysis Plan (SAP).

Pharmacokinetic

All participants treated with at least one dose of study drug with at least 1 reportable concentration of EIDD-will be included in the Pharmacokinetic (PK) population.

6.2.2. Data Handling

Day 1 is defined as the day of first dose of study drug. Relative days after Day 1 are calculated as (assessment date – Day 1 date) + 1. Relative days prior to Day 1 are calculated as (assessment date – Day 1 date). The day prior to Day 1 is Day -1.

All data will be analyzed using nominal study visits as defined in the Study Schedule and eCRF. No visit windows will be applied for summary and analysis. Unscheduled visits will be listed but not tabulated.

Participants who received the same dose (i.e., placebo) across study parts will be combined into the same dose group. Data from the active treatment arms may be combined for analysis, when appropriate in comparison with the pooled placebo group.

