1.2. Primary Safety Objective

Primary Safety Objective:

To evaluate the safety of treatment with EIDD-2801 in participants diagnosed with COVID-19

Primary Safety Endpoints:

- 1. Adverse events (AEs)
- 2. Serious adverse events (SAE)
- 3. Physical examination including vital signs
- 4. Safety laboratory assessments:
 - complete blood counts (CBC) with differentials
 - decrease in hemoglobin (Hgb) by >1 g/dL, or to <9 g/dL
 - decrease in platelet count by $50,000/\mu$ L, or to $<75,000/\mu$ L
 - comprehensive metabolic panels (CMP) including liver function tests
 - increase in aspartate aminotransferase (AST), alanine aminotransferase (ALT), amylase, or lipase to ≥3x the upper limit of normal (ULN)
 - urinalysis
- 5. Electrocardiograms (ECGs)

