6.2.7. Analysis of Other Safety and Clinical Data

Other safety and clinical endpoints will be provided descriptively by dose group and scheduled time of assessment where appropriate. Details will be provided in the SAP.

Version: 7.0

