- f. EIDD-2801 and PBO are to be administered BID on Days 1-5. The first dose will be administered in the morning of Day 1, if possible. If the first dose is given later in the day, the second dose may be given at least 4 hours later on Day 1. If the first dose on Day 1 is given in the late evening, the second dose may be taken on the morning of Day 2, in which case the final dose will be taken on the morning of Day 6. In addition, if a participant misses up to 2 doses during Days 1 to 5, dosing may be extended into Day 6. If discharge occurs prior to completion of study drug dosing (prior to Day 6), study drug will be administered in the hospital on the morning of discharge, and the remainder of the study drug will be dispensed for administration at home by the participant. Procedures will be put into place to ensure study drug compliance (e.g., telephone, eCollection) and drug accountability will be assessed on Days 5 and 8.
- g. One NP swab will be collected from each nostril at each time point for a total of 2 swabs per time point.
- h. Will be obtained at least once on the indicated day AND on the day of discharge from inpatient to outpatient, at the discretion of the investigator in consultation with the sponsor.
- i. Clinical assessments will be ascertained by chart extraction, including number of days in the hospital, maximum O₂ requirements daily, ICU admission and number of days in the ICU, mechanical ventilation and number of days requiring mechanical ventilation, death, and symptom reporting.
- j. If the oxygen saturation value is <92%, the measurement should be repeated once within 30 minutes.
- k. Targeted physical examinations should be done if indicated by an AE or as needed in the judgement of the investigator.
- 1. Laboratory measurements will include CBC with differentials, CMP (including amylase and lipase), and urinalysis.
- m. Results of all chest radiography performed as part of routine clinical care during Study Days 1-28 should be recorded.

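### The nominal-visit rule in Protocol 6.2.2 has no exception for the threshold-based primary safety laboratory endpoints, so a crossing seen only on an unscheduled draw is left out of the tabulated count

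*Protocol*

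**What the plan says.** Protocol 6.2.2 (Data Handling) sets the rule in three consecutive sentences. The first fixes the basis of analysis: "All data will be analyzed using nominal study visits as defined in the Study Schedule and eCRF". The second rules out reassigning a result by its date: "No visit windows will be applied for summary and analysis". The third deals with what falls off the schedule: "Unscheduled visits will be listed but not tabulated". None of them separates efficacy from safety, or by-visit summaries from worst-value counts.

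Protocol 1.2 lists laboratory criteria among the primary safety endpoints. One reads "decrease in hemoglobin (Hgb) by >1 g/dL, or to <9 g/dL". The others are a platelet fall of 50,000/µL or to below 75,000/µL, and AST, ALT, amylase or lipase reaching at least three times the upper limit of normal. None is tied to a visit.

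Two other sections bear on reporting. Section 6.2.7 says "Other safety and clinical endpoints will be provided descriptively by dose group and scheduled time of assessment where appropriate" and leaves details to the SAP. The interim analysis paragraph of 9.2 asks for the cumulative incidence of each type of primary safety endpoint by study arm, with a risk difference and its 95% confidence interval, to inform the sponsor's decision to continue, amend or stop.

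**The concern.** A nominal-visit rule suits by-visit means and changes from baseline, where off-schedule values would blur what each column represents. It does not suit an ever/never criterion. For a limit that can be crossed at any time after dosing, the relevant value is the worst one recorded, whenever it was drawn. Off-schedule draws are also not a random sample of days: extra bloods tend to be taken when something already looks abnormal.

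Suppose a participant's platelets fall to 60,000/µL on an unscheduled Day 12 sample and recover by Day 15. Under 6.2.2 as written, that participant is tabulated as having no platelet event. At stake is the completeness of counts that the protocol itself names as primary safety endpoints and uses in its interim review.

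**Working it through.** The protocol gives no figure on this point, so there is none to reproduce. The check sets the sections side by side and then asks how far the effect can be sized.

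**1. Does the rule reach these endpoints?** Section 6.2.2 covers all data, and the laboratory criteria in 1.2 are data collected at visits. With no visit windows, an unscheduled draw cannot be assigned to a nominal visit. It is therefore listed only.

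**2. Does that conflict with the endpoint?** Cumulative incidence (9.2) counts participants who have ever crossed. Exclusion criterion 4 (3.2) removes hemoglobin below 9 g/dL and platelets below 100,000/µL at entry, so crossing either absolute limit is an on-study event. Removing off-schedule values can only lower the count.

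**3. What still gets through?** Section 8.10.2 requires a worsening grade 3-4 result to be reported as an adverse event, whatever the visit. The same holds for a clinically significant result and for one that leads to interruption, discontinuation or corrective therapy. Section 6.2.6 tabulates these. A grade 1-2 crossing judged not clinically significant, with no action taken, has no such route. The adverse event tables also count coded terms, not the limits in 1.2.

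**4. How much could lie off-schedule?** Post-baseline laboratory days in 7.1 are 3, 5, 8, 15 and 19 (inpatient) and 3, 5, 8, 11 and 28 (outpatient). An episode with onset day s and duration L contains no scheduled draw if no laboratory day d satisfies s ≤ d ≤ s + L − 1. Onset (uniform) and duration are assumptions.

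| Onset | Duration | Inpatient: no scheduled draw | Outpatient: no scheduled draw |
|---|---|---|---|
| Days 2-28 | 3 days | 14/27 = 52% | 14/27 = 52% |
| Days 2-28 | 5 days | 11/27 = 41% | 12/27 = 44% |
| Days 2-14 | 3 days | 4/13 = 31% | 3/13 = 23% |

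For the first row, inpatient onsets on Days 2-8, 13-15 and 17-19 are covered (7 + 3 + 3 = 13), leaving 27 − 13 = 14. Outpatient onsets on Days 2-11 and 26-28 are covered (10 + 3 = 13), again leaving 14.

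These are upper limits on the share that could be seen solely off-schedule, given the assumed onset and duration. An episode with no draw at all is missed under any counting rule. Section 6.2.2 removes only those caught on an unscheduled sample and on no scheduled one.

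**5. What does one omission cost?** Section 6.1 expects 14 or more participants in the higher-dose groups. At 14, one uncounted participant moves incidence by 1/14 = 7.1 percentage points. For illustration, let p be the true crossing rate and u the share of crossers seen only off-schedule; both are assumed. The expected number omitted is 14pu, and the chance of omitting at least one is 1 − (1 − pu)^14.

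- p = 10%, u = 10%: 14 × 0.01 = 0.14 omitted; chance 13%.
- p = 20%, u = 25%: 14 × 0.05 = 0.70 omitted; chance 51%.
- p = 30%, u = 50%: 14 × 0.15 = 2.1 omitted; chance 90%.

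The breadth of that range shows that the document does not fix the size.

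**The case against.** The strongest reply is that the sentence on unscheduled visits follows the nominal-visit and no-window rules and is naturally read as governing by-visit tables. Section 6.2.7 is qualified and defers to the SAP, and a cumulative incidence is by its nature not a by-visit summary. That reading may well be what was meant. It does not remove the point, because 6.2.2 is unqualified and applies to all data. A SAP that counted any post-baseline value would depart from the protocol as it stands.

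A second reply stands in large part: 8.10.2 carries the clinically important crossings into the adverse event tables, and adverse events are themselves a primary safety endpoint. A reader might infer that serious laboratory toxicity would vanish from the tabulated results. The protocol does not support that.

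Two other inferences should be resisted. The 52% in the table is not the share of events lost. It describes sampling frequency, assumes onset as likely in week four as in week one although dosing ends on Day 5 or 6, and holds each participant on one schedule although participants change schedule at discharge. Nor does the discharge-day footnote in the outpatient schedule, "Will be obtained at least once on the indicated day AND on the day of discharge from inpatient to outpatient", extend the problem to laboratory tests. It is attached to swabs, the WHO scale, adverse event reporting and vital signs, not to the Laboratory row, and an assessment that the protocol itself provides for is not obviously unscheduled.

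Finally, scheduled-only counting has a rationale: participants sampled more often have more chances to cross a limit. That is a reason to show both counts, not to show only the smaller one.

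**Conclusion.** The point holds within limits. As written, 6.2.2 omits from the tabulated count of a primary safety laboratory endpoint any participant whose only crossing was on an unscheduled draw. The bias is downward. It falls mainly on grade 1-2 crossings judged not clinically significant, and otherwise on the completeness of the threshold counts, since more serious results reach the adverse event tables.

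Its size cannot be derived from the protocol, which gives neither crossing rates nor the frequency of unscheduled draws. What can be said is that each omission shifts incidence by about 7 percentage points in an arm of 14. To say that a safety signal would be lost goes further than the protocol supports. The primary efficacy comparison, sample size, power and alpha are unaffected.

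This should be corrected, because the text sets a rule that does not fit the endpoints it governs and the correction is cheap.

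**What to change.** Amend 6.2.2 so that the nominal-visit rule, and the listing-only treatment of unscheduled visits, govern by-visit summaries only. Add that the threshold criteria in 1.2, worst post-baseline values and toxicity-grade shifts use all recorded post-baseline results, scheduled or unscheduled. Present the scheduled-only count beside the all-results count, so that any effect of unequal sampling frequency is visible. Apply the same rule to the interim cumulative incidence in 9.2.

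The cost is one sentence in the protocol, matched in the SAP, and a routine programming rule. One matter needs confirming: 4.3.4 ties laboratory recording to the Schedule of Events, and 10.6.3 limits entry to the minimum data that the eCRF requires. The sponsor should check that unscheduled laboratory results are entered, since only recorded values can be counted.

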6.2.3. Handling of Dropouts, Missing Data, and Outliers

Participants who prematurely discontinue from the study without receiving a single dose of study drug or placebo will be replaced. Participants who receive at least a single dose of study drug who prematurely discontinue study drug should continue to undergo regularly scheduled visits, including an end of study visit at Day 28, to evaluate clinical assessments, AEs, and SAEs for the analysis of the primary efficacy endpoint, if there is no swab is available for analysis then the patient's response will be imputed to have a detectable level of SARS-CoV-2 RNA by qPCR (non-response). Longitudinal analyses of secondary endpoints, such as the rate of decline of log₁₀ viral RNA copies/mL for each method of sample collection, will use mixed effect models which are robust for missing data when this is missing completely at random (MCAR) or missing at random (MAR). Missing safety data will generally not be imputed. Details and exceptions will be provided in the SAP. No rules for outlier detection are planned.

